### ***Progression-free survival from rechallenge***

Progression-free survival from rechallenge (per RECIST 1.1 using Investigator assessments) will be defined as the time from **CCI**

CCI

CCI

***Proportion of patients alive at 18 months after randomization (OS18)***

The OS18 will be defined as the Kaplan-Meier (KM) estimate of OS at 18 months after randomization.

***Proportion of patients alive at 24 months after randomization (OS24)***

The OS24 will be defined as the KM estimate of OS at 24 months after randomization.

***Proportion of patients alive at 36 months after randomization (OS36)***

**8.4.2 The OS36 will be defined as the KM estimate of OS at 36 months after randomization.Calculation or derivation of safety variables**

Safety and tolerability will be assessed in terms of AEs (including SAEs), deaths, laboratory data, vital signs, ECGs, and exposure. These will be collected for all patients. Data from all cycles of treatment will be combined in the presentation of safety data. “On treatment” will be defined as assessments between date of start dose and 90 days following discontinuation of study drug(s) (ie, the last dose of durvalumab, tremelimumab, or sorafenib). For AEs, on treatment (or treatment-emergent AEs) will be defined as any AEs that started after dosing or prior to dosing and which worsens following exposure to the treatment.

**8.4.2.1 Adverse events**

AEs observed up until 90 days following discontinuation of the last dose of study drug (durvalumab, tremelimumab, or sorafenib), or until the initiation of the first subsequent therapy following discontinuation of treatment (whichever occurs first) will be used for the reporting of the AE summary tables. Any events in this period that occur after a patient has received further therapy for cancer (following discontinuation of study drug[s]) will be flagged in the data listings.

The safety analysis set will be used for reporting of safety data. A separate data listing of AEs occurring more than 90 days after discontinuation of study drug(s) will be produced. These events will not be included in AE summaries.

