## **6.3 Recording of adverse events**

### **6.3.1 Time period for collection of adverse events**

AEs and SAEs will be collected from the time of the patient signing the informed consent form until the follow-up period is completed (90 days after the last dose of durvalumab±tremelimumab or sorafenib). If an event that starts after the defined safety follow-up period noted above is considered to be due to a late onset toxicity to study drug, then it should be reported as an AE or SAE as applicable.

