**Table 10      Prohibited concomitant medications**

Prohibited medication/class of drug:	Usage:
For all treatment arms	
Any investigational anticancer therapy other than those under investigation in this study	Should not be given concomitantly while the patient is on study drug(s)
mAbs against CTLA-4, PD-1, or PD-L1 other than those under investigation in this study	Should not be given concomitantly while the patient is on study drug(s)
Any concurrent chemotherapy, radiotherapy, immunotherapy, or biologic or hormonal therapy for cancer treatment other than those under investigation in this study	Should not be given concomitantly while the patient is on study drug(s). (Concurrent use of hormones for non-cancer-related conditions [eg, insulin for diabetes and hormone replacement therapy] is acceptable. Local treatment of isolated lesions, excluding TLs, for palliative intent is acceptable [eg, by local surgery or radiotherapy].)
Live attenuated vaccines	Should not be given through 30 days after the last dose of study drug(s)
For all immunotherapy arms	
Immunosuppressive medications including, but not limited to, systemic corticosteroids at doses exceeding 10 mg/day of prednisone or equivalent, methotrexate, azathioprine, and tumor necrosis factor- $\alpha$ blockers	
Should not be given concomitantly or used for premedication prior to infusions. The following are allowed exceptions:
 
 
• Use of immunosuppressive medications for the management of study drug(s)-related AEs
 
• Use in patients with contrast allergies
 
• Use of inhaled, topical, and intranasal corticosteroids
 
 
A temporary period of steroids will be allowed if clinically indicated and considered to be essential for the management of non-immunotherapy-related events experienced by the patient (eg, chronic obstructive pulmonary disease, radiation, nausea).

Drugs with laxative properties and herbal or natural remedies for constipation	Should be used with caution through to 90 days after the last dose of tremelimumab during the study
Sunitinib	Should not be given concomitantly or through 90 days after the last dose of tremelimumab (acute renal failure has been reported with combination therapy of tremelimumab and sunitinib)

Prohibited medication/class of drug:	Usage:

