EGFR TKIs	Should not be given concomitantly Should be used with caution in the 90 days after last dose of durvalumab Increased incidences of pneumonitis (with third generation EGFR TKIs) and increased incidence of transaminase increases (with 1 st generation EGFR TKIs) has been reported when durvalumab has been given concomitantly.
Herbal and natural remedies, which may have immune-modulating effects	Should not be given concurrently unless agreed by AstraZeneca
AE Adverse event; CTLA-4 Cytotoxic T-lymphocyte-associated antigen-4; EGFR TKI Epidermal growth factor receptor tyrosine kinase inhibitor; mAb Monoclonal antibody; PD-1 Programmed cell death-1; PD-L1 Programmed cell death ligand 1; TL target lesion.	

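### AE summary tables stop at first subsequent therapy with no exception for immune-mediated or study-drug-related events, so any that start after a switch but within 90 days of last dose get no by-arm count

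*Protocol*

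**What the plan says.** Section 8.4.2.1 of the protocol sets two limits for the AE summary tables: 90 days after the last dose of study drug, "or until the initiation of the first subsequent therapy following discontinuation of treatment (whichever occurs first) will be used for the reporting". The earlier of the two applies. The section then says how later events are handled. "Any events in this period that occur after a patient has received further therapy for cancer" are to be flagged in the data listings. For events beyond the outer limit, "A separate data listing of AEs occurring more than 90 days after discontinuation of study drug(s) will be produced", and these stay out of the summaries.

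Other sections bear on the same interval:

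- **Section 6.3.1 (collection).** "AEs and SAEs will be collected from the time of the patient signing the informed consent form until the follow-up period is completed", which the protocol puts at 90 days after last dose in every arm. Subsequent therapy does not shorten it.
- **Section 8.4.2 (definitions).** "For AEs, on treatment (or treatment-emergent AEs) will be defined as any AEs that started after dosing", or that started earlier and worsened on exposure. This definition has no cut at subsequent therapy.
- **Section 6.5 (AESIs and imAEs).** It defines these events and gives them no tabulation window of their own.
- **Section 8.5.7 (AE summaries).** AEs are listed by patient and summarized by arm and CTCAE grade. AESIs, imAEs and related events have no separate window. The section leaves further safety summaries to the SAP.

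**The concern.** The cut in Section 8.4.2.1 works by date alone. It treats every event after a switch alike, whether the investigator attributes it to study drug or not, and whether or not it meets the protocol's own definition of an imAE.

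Initiating alternative anticancer therapy ends study drug (Section 3.9), so a switch can fall well inside the 90 days. A hepatitis or pneumonitis that starts after the switch, and is rated as related to study drug, then has its dates, grade and causality recorded (Section 6.3.3) but does not enter the by-arm tables.

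What is at stake is the completeness of the by-arm picture for the class of events the protocol singles out for close monitoring. From the tables set out in Section 8.4.2.1, a reader could not tell how many such events occurred or in which arm. Events during treatment are unaffected, SAEs are still reported, and deaths are a separate safety variable under Section 8.4.2.

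**Working it through.** The protocol states no figure to reproduce and gives no rate to compute with. The check is a matter of logic.

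**Notation.** L is the date of last dose, S the start of first subsequent therapy, and t the start date of an AE.

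**Step 1: what the tables include.** Under Section 8.4.2.1 the upper limit is t ≤ min(L + 90 days, S).

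- If there is no switch, or S falls at or after L + 90 days, the limit is L + 90 days. It then matches the end of collection in Section 6.3.1, and nothing collected up to that day is left out.
- If S falls before L + 90 days, the limit is S. Events with S < t ≤ L + 90 days are collected but not tabulated.

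**Step 2: is there an exception by type or cause?** Sections 8.4.2.1, 6.5 and 8.5.7 contain none. AESIs, imAEs and related AEs in the interval from S to L + 90 days are therefore left out along with the rest.

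**Step 3: where these events do appear.**

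| Output | Includes events with S < t ≤ L + 90 days? |
|---|---|
| AE summary tables (8.4.2.1) | No |
| Separate listing of events beyond 90 days (8.4.2.1) | No, they are too early |
| General listings (8.5, 8.5.7) | Yes, by patient |
| Other significant AEs (8.4.2.2) | Possibly, if non-serious and so judged on expert review |
| SAE reporting (6.4) | Yes, if serious |

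None of these supplies a by-arm count of AESIs/imAEs or related AEs in the interval.

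**Step 4: the flagging sentence.** Read literally, the period referred to is the window just defined. The flagged set must then satisfy both t ≤ min(L + 90 days, S) and t > S, so it is empty. The sentence has content only if the period means the full 90 days, which is almost certainly what was intended.

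**Step 5: size.** A count would need the share of patients switching within 90 days of last dose, the timing of those switches, and the rate of related or immune-mediated onsets afterwards, each by arm. The protocol gives none of these, so neither the number of events nor the direction of any imbalance can be derived.

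**The case against.** The strongest reply has three parts.

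**The cut has a good reason.** Once a new anticancer drug starts, attribution is confounded. Ratings are open-label, and causality against other medication is assessed only for SAEs (Section 6.3.4). This stands, and it is why the existing tables should remain the main analysis.

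**Extra safety tables belong in the SAP.** Section 8.5.7 points there, and the SAP may already contain a full 90-day or imAE table. This stands in part: the point concerns only the protocol's rule. But Section 8.4.2.1 does not leave the window open. It fixes one, and a general pointer to further summaries does not override it.

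**The events are not lost.** They are collected, listed and, if serious, reported. This also stands. What is missing is a count by arm.

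A reader might draw stronger conclusions that the documents do not support:

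- *That Section 8.4.2.1 contradicts Section 8.4.2 or 6.3.1.* It does not. A treatment-emergent definition, a collection window and a tabulation window can differ.
- *That toxicity is under-reported in favour of the immunotherapy arms.* The protocol gives no basis for a direction.
- *That Table 10 or the late-onset clause shows related events are expected after a switch.* The support is weak. The sunitinib entry ("or through 90 days after the last dose of tremelimumab (acute renal failure has been reported with combination therapy of tremelimumab and sunitinib") and the EGFR TKI entry ("Should be used with caution in the 90 days after last dose of durvalumab") concern toxicity with another drug, and so equally illustrate the confounding behind the cut. The clause on events "considered to be due to a late onset toxicity to study drug, then it should be reported as an AE or SAE" applies to events starting after the safety follow-up period, not between a switch and day 90.

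**Conclusion.** The point holds as a modest improvement and does not invalidate the planned AE analysis. Under the rule as stated, immune-mediated and study-drug-related AEs that start after first subsequent therapy but within 90 days of last dose are listed without a by-arm count. The size and between-arm direction cannot be determined from the protocol. The effect is confined to patients who switch before day 90 and to events starting after the switch.

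The conclusion rests on reading Section 8.4.2.1 as written and on the absence of another window in Sections 6.5 and 8.5.7. If the SAP already provides a full 90-day summary of these events, only the protocol text needs aligning. The flagging sentence is a wording slip that affects a listing flag and no result.

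**What to change.** Keep the existing AE tables as the main analysis and add to Section 8.4.2.1:

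> A supplementary summary by treatment arm will present AESIs/imAEs and AEs rated by the investigator as related to study drug, including fatal events, with onset up to 90 days after the last dose of study drug regardless of subsequent anticancer therapy. Events will be shown separately for onset before and after the start of that therapy.

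As a wording correction only, replace *in this period* in the flagging sentence with *within 90 days of the last dose of study drug*.

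The cost is one phrase and a few extra tables. No new data are needed: AE dates and causality are recorded under Section 6.3.3, and the start date of subsequent therapy under Table 4, note f. The downside is that some post-switch events may reflect the next drug. The split by onset shows which events are open to that doubt but does not settle it, so the added tables should be labelled supportive.

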**8.4.2.2 Other significant adverse events**

During the evaluation of the AE data, an AstraZeneca medically qualified expert will review the list of AEs that were not reported as SAEs and AEs leading to discontinuation. Based on

the expert's judgment, significant AEs of particular clinical importance may, after consultation with the Global Patient Safety Physician, be considered other significant AEs (OAEs) and reported as such in the CSR. A similar review of laboratory, vital signs, and ECG data will be performed for identification of OAEs. Examples of these are marked hematological and other laboratory abnormalities, and certain events that lead to intervention (other than those already classified as serious) or significant additional treatment.

#### **8.4.2.3 Safety assessments**

For the change from baseline summaries for vital signs and laboratory data, the baseline value will be the latest result obtained prior to the start of study drug(s).

QTcF will be derived during creation of the reporting database using the reported ECG values (RR and QT) using the following formula:

$$\text{QTcF} = \text{QT}/\text{RR}^{(1/3)} \text{ where RR is in seconds}$$

Corrected calcium product will be derived during creation of the reporting database using the following formulas:

$$\text{Corrected calcium (mmol/L)} = \text{Total calcium (mmol/L)} + ([40 - \text{albumin (G/L)}] \times 0.02)$$

The denominator used in laboratory summaries will only include evaluable patients, ie, those who had sufficient data to have the possibility of an abnormality.

For example:

- If a CTCAE criterion involves a change from baseline, evaluable patients would have both a predose and at least 1 postdose value recorded.
- If a CTCAE criterion does not consider changes from baseline to be evaluable, the patient need only have 1 postdose value recorded.

The denominator in vital signs data should include only those patients with recorded data.

#### **8.4.3 Calculation or derivation of patient-reported outcome variables**

All items/questionnaires will be scored according to published scoring guidelines. All PRO analyses will be based on the FAS.

CCI

Revised Clinical Study Protocol  
Drug Substance Durvalumab (MEDI4736) and tremelimumab  
Study Code D419CC00002  
Version 8.0  
Date 17-June-24

CCI

Revised Clinical Study Protocol  
Drug Substance Durvalumab (MEDI4736) and tremelimumab  
Study Code D419CC00002  
Version 8.0  
Date 17-June-24

CCI

Revised Clinical Study Protocol  
Drug Substance Durvalumab (MEDI4736) and tremelimumab  
Study Code D419CC00002  
Version 8.0  
Date 17-June-24

CCI

Revised Clinical Study Protocol  
Drug Substance Durvalumab (MEDI4736) and tremelimumab  
Study Code D419CC00002  
Version 8.0  
Date 17-June-24

CCI

[figure not shown]
CCI

#### **8.4.3.4 PGIC**

The response options for the PGIC are as follows: Very Much Improved (+3), Much Improved (+2), Minimally Improved (+1), No Change (0), Minimally Worse (-1), Much Worse (-2), and Very Much Worse (-3). No scoring will be done using the assigned numerical values. Instead, the proportion of patients for each response category will be summarized descriptively at each visit.

[figure not shown]
CCI

#### **8.4.5 Calculation or derivation of pharmacokinetic variables**

##### **8.4.5.1 Population pharmacokinetics and exposure-response/safety analysis**

A population PK model will be developed using a non-linear, mixed-effects modelling approach. The impact of physiologically relevant patient characteristics (covariates) and disease on PK will be evaluated. The relationship between the PK exposure and the effect on safety and efficacy endpoints will be evaluated. The results of such an analysis will be reported in a separate report. CCI

##### **8.4.5.2 Pharmacokinetic non-compartmental analysis**

The actual sampling times will be used in the PK calculations. PK concentration data and summary statistics will be tabulated. Individual and mean blood concentration-time profiles will be generated. PK parameters will be determined using standard non-compartmental methods. The following PK parameters will be determined after the first and steady-state

doses: peak and trough concentration (as data allow). Samples below the lower limit of quantification will be treated as missing in the analyses.

#### 8.4.5.3 Immunogenicity analysis

Immunogenicity results will be analyzed descriptively by summarizing the number and percentage of patients who develop detectable ADAs against durvalumab and tremelimumab. The immunogenicity titer and presence of neutralizing ADAs will be reported for samples confirmed positive for the presence of ADAs. **CCI**

#### 8.4.6 Calculation or derivation of biomarker variables

PD-L1 expression, as defined in the secondary objectives, will be assessed for evaluable patients in each cohort according to prespecified criteria that will be detailed in the SAP.

**CCI**

### 8.5 Methods for statistical analyses

The formal statistical analysis of OS (primary endpoint) will be performed for the following efficacy test hypotheses (alternative hypotheses):

- $H_1$ : Difference between durvalumab **CCI** mg plus tremelimumab **CCI** mg **CCI** (Arm C) and sorafenib **CCI** mg **CCI** (Arm D)
- $H_2$ : Durvalumab **CCI** mg monotherapy (Arm A) not inferior to sorafenib **CCI** mg **CCI** (Arm D) with noninferiority margin of 1.08
- $H_3$ : Difference between durvalumab **CCI** mg monotherapy (Arm A) and sorafenib **CCI** mg **CCI** (Arm D)

Efficacy data for Arm B: durvalumab **CCI** mg plus tremelimumab **CCI** mg **CCI** combination therapy arm (which was closed for enrollment with Amendment 4) will be summarized descriptively, but will not be formally analyzed.

Descriptive statistics will be used for all variables, as appropriate, and will be presented by treatment arm. Continuous variables will be summarized by the number of observations, mean, standard deviation, median, minimum, and maximum. Categorical variables will be

summarized by frequency counts and percentages for each category. Unless otherwise stated, percentages will be calculated out of the population total for the corresponding treatment arm.

Baseline will be the last assessment of the variable under consideration prior to the intake of the first dose of treatment, except for efficacy variables. For efficacy variables, baseline is defined as the last visit prior to randomization.

All data collected will be listed. Efficacy and PRO data will be summarized and analyzed based on the FAS (intent-to-treat [ITT] population). PK data will be summarized and analyzed based on the PK analysis set. Safety data will be summarized on the safety analysis set.

Results of all statistical analysis will be presented using a 95% confidence interval (CI) and 2-sided p-value, unless otherwise stated.

**Table 16** details which endpoints are to be analyzed, together with pre-planned sensitivity analyses indicating which analysis is regarded as primary for that endpoint.

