## **8.2 Sample size estimate**

The study will plan to screen approximately 1650 patients in order to randomize approximately 1310 eligible patients in the global study. (This includes 1155 patients randomized to Arms A, C, D with 385 per arm; and approximately 155 patients in Arm B, randomized prior to the closure of this arm. Patients from China enrolled in the global study are included in this figure). Once global enrolment has completed, recruitment into an expansion cohort will continue in China (ie. China Tail) until a total of 180 Chinese patients have been randomized. Patients from China enrolled in the global study and the China Tail will be included in a China cohort. Details of the China cohort and analysis plan will be outlined in a China specific amendment and SAP. Patients will be randomized 1:1:1:1 to durvalumab [redacted] mg monotherapy (Arm A), durvalumab [redacted] mg plus tremelimumab [redacted] mg [redacted] combination therapy (Arm B), durvalumab [redacted] mg plus tremelimumab [redacted] mg [redacted] combination therapy (Arm C), or sorafenib [redacted] mg [redacted] (Arm D). Following Amendment 4 Arm B will be closed for enrollment therefore new patients will be randomized in a 1:1:1 ratio into Arm A, Arm C, and Arm D.

The study is sized to characterize the OS benefit of Arm C vs. Arm D.

The sample size estimation assumes an exponentially distributed OS and a 2-month delay in separation of the OS curves for Arm C vs. Arm D, hence the use of average HR (0.70 for Arm C vs. Arm D). A non-uniform accrual (weight=2) of patients with a duration of 22 months is assumed when estimating the analysis times with a follow-up duration of 15.5 months and a total duration of 37.5 months. No adjustment has been included for dropouts.

For the efficacy comparisons, the median OS for sorafenib (Arm D) is assumed to be 11.5 months, with an 18-month OS rate of 33.8%.

***Durvalumab [REDACTED] mg plus tremelimumab [REDACTED] mg [REDACTED] (Arm C) versus sorafenib [REDACTED] mg [REDACTED] (Arm D) - OS in FAS intent-to treat (ITT)***

The assumed OS treatment effect is an average HR of 0.70 for Arm C versus Arm D. This translates to an increase in median OS from 11.5 months to 16.5 months and in the 18-month OS rate from 33.8% to 46.8% in Arm C versus Arm D.

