#### 8.3.1 Full analysis set

The FAS will include all randomized patients. The FAS will be used for all efficacy analyses (including PROs). Treatment arms will be compared on the basis of randomized study drug(s), regardless of the study drug(s) actually received. Patients who were randomized but did not subsequently go on to receive study drug(s) are included in the analysis in the treatment arm to which they were randomized.

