#### **8.5.4.4 PGIC**

Responses on the PGIC will be summarized descriptively as number of patients and corresponding percentages for each category in the questionnaire at each visit by treatment arm.

CCI

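### By-visit PGIC percentages fall under the all-randomized default denominator, so attrition dilutes every answer category, and by more in the arm that loses more patients

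*Protocol*

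**What the plan says.** The default is in Protocol Section 8.5: "Unless otherwise stated, percentages will be calculated out of the population total for the corresponding treatment arm".

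The population is fixed in two steps. Section 8.4.3 states "All PRO analyses will be based on the FAS", and Section 8.3.1 states "The FAS will include all randomized patients". Section 8.2 plans "1155 patients randomized to Arms A, C, D with 385 per arm".

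PGIC is described twice. Section 8.4.3.4 rules out numerical scoring and says that "the proportion of patients for each response category will be summarized descriptively at each visit". Section 8.5.4.4 asks for "number of patients and corresponding percentages for each category in the questionnaire at each visit by treatment arm". Neither names a denominator.

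Exception clauses do exist elsewhere. Section 8.4.2.3 restricts laboratory summaries to evaluable patients and says of vital signs: "The denominator in vital signs data should include only those patients with recorded data".

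Tables 2 and 4 schedule PGIC every 8 weeks to week 48 and every 12 weeks after that. Collection stops about 3 months after treatment discontinuation or progression. Section 8.5.4 provides a separate table of questionnaire compliance by visit.

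**The concern.** PGIC is recorded visit by visit in a population that shrinks by design. Patients die, and others pass the end of PGIC collection. With all randomized patients as denominator, each printed percentage is the product of two things: the share of the arm still answering, and the share of those answering who chose that category. A reader comparing arms cannot separate the two from the percentage alone.

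The protocol expects the arms to differ in survival, so unequal attrition is the planned scenario. Two arms whose responders feel exactly the same would print different percentages, and the difference would grow with follow-up. Section 5.3.1.5 presents PGIC as a measure of the overall impact of treatment, so a reader may well look at this table for that purpose.

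This is a stated rule that does not suit by-visit data. It is more than a detail left open for the SAP, and the exceptions in 8.4.2.3 show that the authors saw the same need for other repeated measurements.

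**Working it through.** **Inputs from the protocol (Section 8.2).** 385 patients per arm; exponential survival; median OS 11.5 months in Arm D and 16.5 months in Arm C; 18-month OS 33.8% and 46.8%.

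**Assumptions not in the protocol.** Every survivor answers, so deaths are the only loss. The share of responders answering worse is the same in both arms: 30%, with a range of 20% to 40%.

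**Reproducing the protocol's figures.** S(t) = exp(−ln 2 × t / median).
- Arm D at 18 months: exp(−ln 2 × 18/11.5) = 33.8%. Stated: 33.8%.
- Arm C at 18 months: 46.8% using HR 0.70, or 46.9% from the 16.5-month median. Stated: 46.8%.

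**Formula.** Printed percentage = (share of arm answering) × (share worse among responders). The responder-based percentage is the second factor alone.

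**Week 48** (48 × 7 / 30.44 = 11.04 months), a scheduled PGIC visit:
- Alive: Arm D 51.4%, Arm C 62.9%. These are also the totals to which the seven categories add, about 0.514 × 385 = 198 and 0.629 × 385 = 242 respondents.
- Worse at 30%: D 0.30 × 51.4% = 15.4%; C 0.30 × 62.9% = 18.9%.
- Gap (C minus D) at 20%, 30% and 40% worse: 2.3, 3.4 and 4.6 points.

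**18 months**, the time of the protocol's stated OS rates:
- Worse at 30%: D 0.30 × 33.8% = 10.1%; C 0.30 × 46.9% = 14.1%.
- Gap at 20%, 30% and 40%: 2.6, 3.9 and 5.3 points.

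**Earlier visits.** The gap is smaller: 0.6 to 1.2 points at week 8 and 1.5 to 3.0 points at week 24.

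**Delayed separation.** With the protocol's 2-month delay and the Arm C median held at 16.5 months, 62.0% of Arm C is alive at week 48. The 30% case then prints 18.6% instead of 18.9%.

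**Other categories.** The same factor applies to all of them. If 40% of responders were improved, week 48 would print 20.6% in D and 25.2% in C. The ratio of worse to improved stays at 0.75 in both arms.

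**With responders as denominator.** 30% in both arms (or 20% in both, or 40% in both), so the gap is zero at every visit.

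**The case against.** **The table is not percentages alone.** Section 8.5.4.4 also requires the number of patients in each category, and compliance is tabulated by visit. Adding the seven counts gives the respondents, so a careful reader can rescale. This stands and limits the harm, but the percentages as printed remain diluted.

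**The all-randomized denominator has a meaning.** It can be read as the share of randomized patients reporting a given answer at that visit, and it keeps the randomized comparison. A responder denominator conditions on survival and completion: if sicker patients drop out first, the arm with more dropout looks better. This is a fair point, and the change does not cure selective dropout. It removes the mechanical dilution, and the selection becomes visible when the numbers randomized, expected and responding stand beside the percentages.

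**This is SAP detail, and parts of the PRO text are blacked out.** The SAP was not available for this check, and a PRO-wide denominator could stand in a redacted part. The two PGIC sections, however, are legible and state none, while the rule in 8.5 is explicit and applies in the absence of one.

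**PGIC carries little weight.** It is listed among the other PROs, is absent from the secondary objectives and is not tested. This stands too.

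**A stronger reading.** A reader might infer that the rule flatters the arm with faster progression or death because fewer of its patients appear worse. The protocol does not support that: improved answers fall by the same factor, so the dilution has no one-sided direction.

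**Conclusion.** The point holds as a minor correction. As the protocol is written, by-visit PGIC percentages use all randomized patients, their total falls with the share still answering, and every category is diluted more in the arm with more attrition.

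The size of about 2 to 5 points between Arms C and D applies to week 48 and 18 months. It rests on the protocol's OS assumptions, on deaths as the only loss, and on an assumed 20% to 40% of responders answering worse in both arms. In practice collection also ends after progression or discontinuation. The response shares will then be lower than survival, and the gap could be larger or smaller, depending on how far those shares differ between arms.

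It would be wrong to infer that a trial conclusion is at risk. PGIC is descriptive, no test of it is planned, and neither type I error nor any OS result depends on it.

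**What to change.** Add to Section 8.5.4.4: PGIC percentages at each visit use as denominator the patients with a PGIC response at that visit, and the numbers randomized, expected to respond and responding are shown beside them for each arm. Section 8.4.3.4 can refer to that sentence.

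The cost is one sentence, a changed denominator and three count columns in one table. The compliance table already requires most of those counts. The small downside is that responder percentages condition on survival and completion, which the displayed counts let the reader judge.
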